### 7.4.3 Proportional hazards assumption violated

The proportional hazards assumption will be explored by plotting log (-log (survival function)) against the log of time by treatment group and checked for parallelism. The interaction of treatment with log of time will be included in the model described above for an exploratory analysis. Further, Schoenfeld residuals for each covariate and treatment will be plotted against time and log (time).

In case the proportionality assumption is violated for treatment, an attempt will be undertaken to identify groups of patients for which the proportionality assumption holds and a stratified Cox regression will be performed. The HR and corresponding CIs will be obtained from the stratified Cox model.

In addition a piecewise Cox model assuming proportional hazards in a series of consecutive time intervals as proposed by Collett (6) will be investigated.

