## **7.4 PRIMARY ENDPOINT**

The primary estimand of this trial is the hazard ratio of the time to first event of adjudicated HHF or adjudicated CV death between empagliflozin 10 mg and placebo in the population of patients with heart failure with reduced ejection fraction. The primary comparison will be made regardless of changes of treatment (including discontinuation of trial medication) until completion of the planned treatment phase. For clarification, this excludes events and time at risk after the protocol-specified treatment discontinuation for patients that complete the treatment period according to protocol.

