### **7.4.1 Primary analysis of the primary endpoint(s)**

As the primary endpoint, time to the first event of adjudicated HHF or adjudicated CV death will be reported in days. The primary analysis will be based on RS, using all data available until completion of the planned treatment phase, including the data after end of treatment for patients not completing the treatment phase as planned.

The primary endpoint will be displayed using cumulative incidence function (CIF) curves and expressed as the hazard ratio with associated two-sided 95% confidence intervals (CIs) and two-sided CIs based available alpha-level for the analysis.

For the interim analysis and final analysis, the following Hwang, Shih and De Cani  $\alpha$ -spending function at information fraction  $t_k$  with parameter  $\gamma = -8$  will be used:

$$\alpha^*(\gamma, t_k) = \min \left\{ \alpha, \quad \alpha \frac{1 - e^{-\gamma t_k}}{1 - e^{-\gamma}} \right\} = \min \left\{ 0.025, \quad 0.025 \frac{1 - e^{8t_k}}{1 - e^8} \right\}$$

The alpha levels are expected to be 0.001 and 0.0248 (one-sided) for the interim and final tests respectively, when the interim analysis occurs at the time of 60% information.

Estimator and corresponding confidence intervals will not be corrected for interim analysis.

The primary endpoint will be analysed using Cox regression, with factors of treatment (empagliflozin, placebo), region (North America, Latin America, Europe, Asia and “other” including India, South Africa and Australia), baseline status of diabetes (diabetes, prediabetes, no diabetes), age (continuous), sex, left ventricular ejection fraction (LVEF) ( $\leq 30\%$ ,  $> 30\%$  to  $\leq 35\%$ ,  $> 35\%$ ) and eGFR (CKD-EPI)cr at baseline (continuous). Since the stratification factors are included in the model as covariates, no stratified Cox regression will be used.

Breslow’s method will be used for dealing with ties.

The individual relevant components of the composite will be summarized descriptively. In this descriptive analysis of the relevant component for the composite, CV death after HHF will not be counted. In all other analyses of CV death alone defined in this document, all CV deaths will be counted, disregarding any earlier events.

A hierarchical testing procedure will be followed for the assessment of the primary and key secondary endpoints. For all endpoints, superiority of empagliflozin vs. placebo will be evaluated using a two-sided test.

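### If proportional hazards fails for treatment, SAP 7.4.3 takes the HR from strata chosen after unblinding, with no search rule and no stated status relative to the primary result

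*SAP*

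**What the plan says.** SAP 7.4 defines the target: "The primary estimand of this trial is the hazard ratio of the time to first event of adjudicated HHF or adjudicated CV death". SAP 7.4.1 estimates it with a covariate-adjusted Cox model. Because the randomisation factors are already covariates, it adds that "no stratified Cox regression will be used".

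SAP 7.4.3 covers departures from proportional hazards:

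- **Check.** Log(-log) survival is plotted "against the log of time by treatment group and checked for parallelism". Schoenfeld residuals are plotted for treatment and each covariate. There is also a formal term: "The interaction of treatment with log of time will be included in the model described above for an exploratory analysis". No threshold is attached to any of these.
- **First response.** If the assumption fails for treatment, "an attempt will be undertaken to identify groups of patients for which the proportionality assumption holds". A stratified Cox regression follows, and "The HR and corresponding CIs will be obtained from the stratified Cox model".
- **Second response.** "In addition a piecewise Cox model assuming proportional hazards in a series of consecutive time intervals" will be investigated. The intervals are not given.

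Protocol 7.3.1 contains no such fallback. Protocol 4.1.5.1 keeps those conducting and analysing the trial blinded until after database lock.

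**The concern.** The remedy does not match the trigger. The trigger is non-proportionality for treatment. A model stratified on patient groups gives each group its own baseline hazard but keeps a single treatment log HR, constant over time. If the drug's effect grows or fades with time in all patients, no choice of strata changes that.

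The trigger could well be met. The primary comparison runs through treatment stops and restarts (SAP 6.1 and 7.4), which could make the HR drift. The documents do not predict that it will.

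The groups are also chosen from the data. The SAP does not say in words that the search is unblinded, but plots by treatment arm cannot be drawn without the codes. With no criterion, candidate list or stopping rule, two competent analysts could report different HRs, each with an interval that takes no account of the search.

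Finally, the section does not give the status of this HR. Where the SAP wants a fallback to be confirmatory it says so, as for the joint frailty model in 7.5.1.1. Here a reader of the trial report could not tell which HR is the trial's result.

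**Working it through.** **Step 1: the plan's own figures.** These do not test the point, but they anchor the simulations. Inputs (Protocol 7.7, SAP 9.6): HR 0.80, two-sided alpha 0.05, power 90%, 1:1 allocation, placebo rate 15% per year, 18 months' accrual plus 20 months' follow-up.

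- Events: 4 × (1.960 + 1.282)² / (ln 0.80)² gives 845, against 841 stated.
- Patients: with a placebo hazard of -ln(0.85) per year, the average event probability is 0.2958, and 841 / 0.2958 = 2843, against 2850 stated.
- Interim: the spending function with gamma -8 at 60% information gives one-sided levels of 0.00101 and 0.02483 (stated 0.001 and 0.0248) and power of 89.87% (SAP 89.98%).

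**Step 2: what stratifying does.** In stratum s the hazard is h_s(t) × exp(b × treatment). The functions h_s differ freely between strata; b does not depend on t. So a true b(t) shared by all patients stays misspecified whatever the strata.

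**Step 3: simulations.** Each trial had 2850 patients with the design inputs above and ten binary baseline factors, giving 10 single and 45 paired stratifications (55 in all). The Cox model contained treatment only. PH was tested by Schoenfeld residuals against log time at |z| > 1.96. The effect patterns are assumptions, not taken from the documents.

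*A. Effect changes with time:* HR 0.65 in year 1 and 0.95 afterwards in everyone; three factors mildly prognostic; 400 trials.

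| Model | Mean HR | PH rejected |
|---|---|---|
| Unstratified | 0.81 | 49% |
| Stratified on a prognostic factor | 0.81 | 50% |
| Best PH fit of 55 | 0.81 | 47% |

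The Monte Carlo standard error is √(0.49 × 0.51 / 400) = 0.025, so nothing was repaired. Within a trial the HR ranged over the 55 choices by 0.016 on average (maximum 0.046).

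*B. Omitted prognostic group:* HR 0.60, constant within each of two groups; one group at 8 times and the other at 0.3 times the base hazard (ratio 8 / 0.3 ≈ 27); 400 trials.

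| Model | Mean HR | PH rejected |
|---|---|---|
| Unstratified | 0.77 | 88% |
| Stratified on that group | 0.60 | 5% |
| Best PH fit of 55 | 0.60 | 2.5% |

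Here PH is restored, and the HR changes because it is now conditional on the group. The within-trial range over the 55 choices averaged 0.18 (maximum 0.28).

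*C. Type I error:* no treatment effect, nominal 0.05, 3000 trials, with the selection applied in every trial.

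| Choice of strata | Rejection rate |
|---|---|
| None | 0.049 |
| Best PH fit | 0.049 |
| Most significant | 0.071 |

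The Monte Carlo standard error is √(0.05 × 0.95 / 3000) = 0.004. A separate 1000-trial set gave 0.046, 0.044 and 0.069.

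**The case against.** The strongest reply is that 7.4.3 is a diagnostic section and nothing more. Most of its language is exploratory, and it never says that its HR replaces the primary one or supplies a p-value to the hierarchy. Protocol 7.4 ties the interim decision to the primary Cox model. The 7.4.1 sentence ruling out stratified Cox concerns the randomisation factors, not PH diagnostics, so it does not contradict 7.4.3. The same section plans a piecewise Cox model, which does address an effect that changes with time. Stratifying can also be the right tool: log NT-proBNP and HHF in the last 12 months are outside the primary model and enter only a sensitivity model in 7.4.2, so an omitted prognostic factor is a realistic cause of apparent non-proportionality.

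All of this stands, and it rules out several stronger readings that a reader might infer:

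- **That stratification never restores PH.** Scenario B shows that it can.
- **That the searched HR becomes the confirmatory result.** The text does not say so.
- **That type I error is inflated.** Choosing strata by PH fit, the closest reading of the SAP, left it at 0.049. The 0.071 needs selection by significance, which the SAP does not propose, although it gives no rule excluding it.

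In scenario A the spread is also small. At 841 events the standard error of the log HR is about 2 / √841 = 0.069, or 0.81 × 0.069 = 0.056 on the HR scale, against a mean spread of 0.016.

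The reply does not meet two points. The sentence on the source of the HR carries no supportive label, and the search has no rule.

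**Conclusion.** The point holds as a defect of specification. Followed literally, 7.4.3 can yield an HR selected after unblinding by an unstated rule. Where the treatment effect itself changes with time, that HR is no nearer to proportionality than the planned one (49%, 50% and 47% rejection). Where a strong prognostic group was left out, stratifying can cure the violation, but the HR can then differ materially from the pre-specified one (0.77 against 0.60) and answers a different conditional question.

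The second size is illustrative and towards the upper end. It rests on a 27-fold risk ratio between groups and on an unadjusted comparator; the 7.4.1 model adjusts for several covariates, so a real shift would probably be smaller. That the search is unblinded is an inference from the by-arm plots and the blinding rule, though a firm one. Any effect on the confirmatory test is not established. This is a worthwhile, inexpensive improvement and does not threaten the primary analysis in 7.4.1.

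**What to change.** Amend SAP 7.4.3 before unblinding:

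1. State that the 7.4.1 Cox HR, confidence interval and p-value remain the primary result whatever the PH check shows.
2. Remove the sentence taking the HR from the stratified model. Alternatively, keep that analysis, label it supportive, and limit it to factors named in advance; log NT-proBNP and HHF in the last 12 months are natural candidates because 7.4.2 already uses them.
3. Fix the intervals of the piecewise Cox model, for example 0-6, 6-12 and beyond 12 months.
4. Add, as a supportive summary, the difference in restricted mean event-free time at a fixed time point. Recruitment may continue until 6 months before the event target is expected, so choose a time point with enough patients still at risk.

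The cost is SAP wording and minor programming, since the piecewise model is already planned. Dropping the stratified analysis altogether would lose something useful in the omitted-factor case, which is the argument for keeping it as supportive.

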#### 7.4.4 Subgroup analyses

Subgroup variables will be explored as described in [Section 6.4](#) for the primary endpoint. The HR between the two treatments along with 95% CI and the p-value for test of treatment equality within each category of the subgroup as well as the p-value for the subgroup-by-treatment interaction will be estimated by the Cox proportional hazard model including the same covariates as in the primary analysis of primary endpoint, the subgroup variable if not part of the covariates of the primary analysis model, and subgroup-by-treatment interaction. If the subgroup variable is a categorization of a continuous covariate, this covariate will be dropped from the subgroup model. A forest plot will be presented with the estimated HR and the two-sided 95% CI for each subgroup category. The CIF plots will also be presented for each subgroup category.

For the baseline eGFR subgroup with five categories (refer to [Section 9.4](#)), the interaction p-values will be conducted as trend tests, taking into account that the subgroup categorizations are ordered. Assuming the difference between the adjacent subgroup is the same, each subgroup is coded as numeric value ordinally and fitted into the model as numeric covariate. The model also includes terms of subgroup variable and subgroup-by-treatment interaction.

If there are less than 14 patients with events in one subgroup, then this subgroup will not be included in the model. If this leaves only one subgroup, the subgroup analysis will not be conducted.

For the continuous covariates, baseline eGFR and age, the influence of the covariate will also be investigated on a continuous scale. For this purpose the continuous covariate will be added to the model if not already included and the interaction term of the continuous covariate and treatment will additionally be included into the model. The hazard ratio depending on the continuous covariate will be plotted and the interaction p-value will be reported.

## 7.5 SECONDARY ENDPOINTS

### 7.5.1 Key secondary endpoints

#### 7.5.1.1 Primary analysis of the key secondary endpoints

##### **Occurrence of adjudicated HHF (first and recurrent)**

Hospitalisation for heart failure will be analysed by a joint frailty model (JFM) that accounts for the dependence between recurrent HHF and CV death (7). The primary analysis will be based on all data available until completion of the planned treatment phase, including the data after end of treatment for patients not completing the treatment phase as planned.

Define  $T_{i0} = 0$  and let  $T_{i1}, T_{i2}, \dots, T_{iN_i}$  be the recurrent event times for person  $i$ , where  $N_i$  is the number of recurrent HHF events before  $X_i = \min(C_i, D_i)$ , the minimum of an independent censoring time  $C_i$  and a dependent CV death time  $D_i$ . The JFM is defined through the hazard functions for the recurrent event process and CV death

$$\begin{aligned} r_i(t | \omega_i) &= \omega_i \exp\{\beta_1 z_i\} r_0(t) \\ \lambda_i(t | \omega_i) &= \omega_i^\alpha \exp\{\beta_2 z_i\} \lambda_0(t) \end{aligned}$$

The recurrent heart failure hospitalisations intensity function for the  $i$ -th patient conditional on the patient specific random frailty,  $\omega_i$ , is given by  $r_i$  and is proportional to the baseline intensity function,  $r_0$ . The conditional hazard function for time to CV death for patient  $i$  is given by  $\lambda_i$ , with the baseline hazard given by  $\lambda_0$ , and  $\beta_1, \beta_2$  are  $p \times 1$  vectors of regression coefficients associated with vectors of covariates  $z_i$ . The same covariates as for the analysis of the primary endpoint will be used, e.g.  $\beta_1$ =treatment (empagliflozin, placebo),  $\beta_2$ =region (North America, Latin America, Europe, Asia and “other” including India, South Africa, and Australia),  $\beta_3$ =baseline status of diabetes (diabetes, prediabetes, no diabetes) etc.

Patient specific independent random effects are denoted by  $\omega_i$  and are assumed to follow a gamma distribution with mean 1 and variance  $\theta$ . The correlation of the recurrent events is quantified by  $\theta$ , with higher values corresponding to greater within-patient correlation and also greater between-patient variability. The parameter  $\alpha$  determines the relationship between the recurrent heart failure hospitalisations and time to CV death. When  $\alpha < 0$ , higher frailty will result in a greater risk of recurrence and lower risk of terminal event (i.e. a negative correlation between the frailties), and when  $\alpha > 0$ , higher frailty will result in a greater risk of recurrence and is associated with a higher risk of CV death (i.e. a positive correlation between the frailties).

Let  $t_{ij}$  and  $x_i$  be the observed recurrent event times and follow-up, respectively. Denote by  $\delta_{ij}$  and  $\Delta_i$ , the indicator of the recurrent event at time  $t_{ij}$  and the indicator of CV death at time  $x_i$ , respectively. The likelihood for person  $i$  is then given by the following:

$$L_i = \int_{\omega_i} \prod_{j=1}^{N_i} [\omega_i r_i(t_{ij})]^{\delta_{ij}} \exp \left\{ \int_0^{x_i} \omega_i r_i(t) dt \right\} [\omega_i^\alpha \lambda_i(x_i)]^{\Delta_i} \exp \left\{ \int_0^{x_i} \omega_i^\alpha \lambda_i(t) dt \right\} f_\theta(\omega_i) d\omega_i.$$

Adopting piecewise constant hazards for the recurrent events and CV death allows estimation of the likelihood by Gaussian quadrature. The implementation of the used adaptive Gaussian quadrature techniques is incorporated into Proc NLMIXED of SAS 9.4. SAS Code following the strategy outlined in [\(9\)](#) will be used.

The size of the pieces for the piecewise constant hazards can be different and are determined separately for the terminal as well as recurrent event process with 10 pieces each. The nodes are defined by the empirical deciles of the recurrent or terminal events, respectively.

The joint frailty model using the multiplicative parametrization with non-normal random effects will be fitted using a likelihood-reformulation method [\(10\)](#).

To improve convergence of the model, linear covariates (in case no interaction with treatment is modelled) will be standardized prior inclusion into the analysis and starting values for the model parameters will be determined using the following procedure:

- 1) An exponential model will be fitted for the terminal event and a poisson regression model for the recurrent event process including the same covariates that are included in the final joint frailty model to get initial starting values for all parameters.
- 2) A simplified model without random effect  $\omega$  which is otherwise equal (regarding covariates, baseline hazards) to the joint frailty model is fitted using the values from step (1) as starting values for the parameters. The estimated coefficients from the simplified model will then be used as starting values for the parameters of the piecewise-constant joint frailty model.

The joint model gives two distinct hazard ratios:

$HR_{HHF} = \exp\{\beta_{11}\}$  is the hazard ratio associated with the effect of treatment on the recurrent event rate of HHF, and  $HR_{CVD} = \exp\{\beta_{21}\}$  is the CV death hazard ratio.

Estimates and 95% CI for the hazard ratios and for  $\alpha$  (relationship between the recurrent heart failure hospitalisations and CV death) will be given.

The following sensitivity analyses will be conducted

- Based on the TS, including only any events up to 30 days after treatment discontinuation
- Instead of CV-death, jointly model HHF with all-cause mortality as the terminal events (otherwise same model as initially described)
- The endpoint will be additionally evaluated based on investigator defined events for HHF and CV death (otherwise same as initially described model).
- A parametric joint gamma-frailty model will model the recurrent event component using a Poisson distribution and model the CV mortality component using an exponential distribution, conditional on the frailty parameter. Individual frailties are again assumed to follow a Gamma distribution. Thus HHF rates follow a negative binomial distribution and times to CV death follow a Lomax distribution (see [\(8\)](#)) (otherwise – e.g. covariates - same as initially described model).
- The analysis will be repeated to include all events up to individual trial completion including the follow-up period (otherwise same as initially described model).
- The analysis will be repeated to include only confirmed HHF which meet the CDISC guidance criteria for hospitalization for heart failure (i.e., confirmed by adjudication committee, but excluding those missing a physical sign or laboratory test, or both).
- A COVID-19 sensitivity analysis will be conducted. The analysis will be repeated to include all events up to cutoff dates prior to COVID-19 outbreak – cutoff (censoring) dates are 30Nov2019 for China and 31Dec2019 for all other countries.

In case the semi-parametric joint modelling cannot converge numerically with the existing SAS procedures, the parametric joint gamma-frailty model as described above may be used instead for the confirmatory analysis.

The number of HHF events per patients will be summarized descriptively. Additionally a negative binomial model will be fitted to the data of recurrent HHF. This will be done once including only treatment as covariate and once including all covariates as the primary model. Rate ratio and confidence intervals of both models will be reported.

The mean cumulative incidence will be displayed for adjudicated recurrent HHF.

Subgroup analyses will be explored as outlined in [Section 6.4](#) for adjudicated recurrent HHF. For subgroup analyses the term of subgroup (if not already part of the model) and subgroup by treatment will be added to the model of the recurrent event. If the subgroup variable is a categorization of a continuous covariate, this covariate will be dropped from the subgroup model.

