Variable	Categorization	Demo-graphics 	Subgroups for Efficacy endpoints 	Safety 
Cause of HF	Ischemic Hypertensive Valvular heart disease Diabetic Alcoholism Idiopathic Other	X		
	Ischemic Non-ischemic		X	
Time since diagnosis of HF	<= 1 year, 1-5 years, > 5 - 10 years, >10 years	X		
NYHA at baseline	I/II/III/IV	X		
	II vs. III/IV		X	
Heart failure physiology	LVEF ≤ 30% and NT-proBNP < median  ; LVEF ≤ 30% and NT-proBNP ≥ median  ; LVEF > 30%		X	
Baseline use of ACE-inhibitor, ARB or ARNi	Yes / No	X#		X (renal AEs, volume depletion AEs and hypotension AEs)
Baseline use of MRA	Yes / No	X#	X	
Baseline use of diuretics	Yes / No	X#		X (renal AEs, volume depletion AEs and hypotension AEs)
Baseline use of loop or high-ceiling diuretics	Yes / No	X#		X (renal AEs, volume depletion AEs and hypotension AEs)
Baseline use of ARNi	Yes / No	X#	X	X (renal AEs, volume depletion AEs and hypotension AEs)

 The column demographics shows categories shown in the overall demographics. Demographics are not planned by subgroup.

 Subgroups planned for the primary endpoint, time to cardiovascular (CV) death, time to first HHF, HHF (first and recurrent), renal slope.

 X means subgroups planned for overall AE summaries, AEs by SOC and PT, SAEs, AEs leading to discontinuation, decreased renal function, UTI, genital infection, volume depletion, hypotension and bone fracture.

 Overall means overall AE summaries, AEs by SOC and PT, SAEs and AEs leading to discontinuation

 Median calculated separately for baseline atrial fibrillation or atrial flutter (determined by ECG) / no baseline atrial fibrillation and atrial flutter (determined by ECG)

+ Region categorization: see [Table 9.1.1](#).

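### Recurrent-HHF subgroup models: as worded, the subgroup terms enter only the HHF hazard, so one CV-death treatment HR is imposed on all subgroups and the exploratory HHF subgroup HRs can be biased

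*SAP*

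**What the plan says.** SAP 7.5.1.1 models recurrent HHF and CV death as two hazards that share a patient frailty. The frailties "are assumed to follow a gamma distribution with mean 1 and variance" theta, and the parameter alpha "determines the relationship between the recurrent heart failure hospitalisations and time to CV death". Both hazards carry one covariate vector: "The same covariates as for the analysis of the primary endpoint will be used". Treatment has a separate coefficient in each: "The joint model gives two distinct hazard ratios", one for HHF and one for CV death.

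For subgroups, the section adds the subgroup main effect, unless it is already a covariate, and says that "subgroup by treatment will be added to the model of the recurrent event". The next sentence reads: "If the subgroup variable is a categorization of a continuous covariate, this covariate will be dropped from the subgroup model". It does not say which of the two hazards it means.

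Footnote 2 to Table 6.4:1 lists the endpoints concerned: "Subgroups planned for the primary endpoint, time to cardiovascular (CV) death, time to first HHF, HHF (first and recurrent), renal slope". CV death by subgroup is therefore also analysed on its own.

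**The concern.** Elsewhere in SAP 7.5.1.1 *recurrent event* means the HHF process, and CV death is the *terminal event*. The section keeps the two apart when it chooses the pieces of the baseline hazards and when it sets starting values (Poisson for one, exponential for the other). In that vocabulary, the subgroup terms go into the HHF hazard and not into the CV-death hazard.

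The main model lets treatment act separately on HHF and on CV death. The subgroup model would let it vary by subgroup for HHF but fix it for CV death. Suppose alpha is positive and, in one subgroup, treated patients die more often than the common CV-death HR predicts. The model can account for the excess only by giving those patients higher frailty. Their HHF counts are then judged against a higher expected rate, so the HHF HR in that subgroup is pulled down. In the other subgroup it is pulled up. At stake is the credibility of the HHF subgroup display in the situation a joint model is meant to handle.

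**Working it through.** **Plan's own figures.** The documents give no figure for these subgroup models. The design size is not in dispute and reproduces: 4 × (1.960 + 1.282)² / (ln 0.80)² gives 845 events, against 841 in SAP 9.6.

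**Inputs from the documents.** Joint gamma-frailty model (SAP 7.5.1.1); 1:1 allocation (Protocol 7.6); 20 to 38 months of follow-up, from 18 months accrual plus 20 months follow-up, and about 3600 patients (SAP 9.6).

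**Assumed inputs.** Theta 1.5 or 2.5; alpha 0.7, with 0 as a control; a 50/50 binary subgroup; baseline rates of 0.20 per year for HHF and 0.09 for CV death at frailty 1 (0.065 for CV death in the alpha = 0 control); constant baseline hazards, where the SAP uses 10 pieces; no other covariates. The true HHF treatment HR is 0.70 in both subgroups, so the true ratio of HHF HRs is 1.00.

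**Method.** One dataset of 40,000 patients per setting, fitted twice by maximum likelihood: with subgroup terms in both hazards, and with them in the HHF hazard only.

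Shift = ln(ratio, HHF hazard only) − ln(ratio, both hazards). Ratios are the HHF HR in the second subgroup over that in the first. The SE is that of the interaction scaled to 3600 patients, about 0.16 in the theta 2.5, alpha 0.7 settings.

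| Theta, alpha | CV-death HR in the two subgroups | Ratio, both hazards | Ratio, HHF only | Log shift | Shift in SE |
|---|---|---|---|---|---|
| 2.5, 0.7 | 0.85, 0.85 | 0.961 | 0.960 | -0.001 | 0.00 |
| 2.5, 0.7 | 0.85, 0.85, with subgroup main effect* | 1.053 | 1.066 | +0.012 | 0.07 |
| 2.5, 0 | 0.60, 1.10 | 1.045 | 1.047 | +0.002 | 0.01 |
| 1.5, 0.7 | 0.70, 1.00 | 1.064 | 1.014 | -0.048 | 0.34 |
| 2.5, 0.7 | 0.70, 1.00 | 0.980 | 0.919 | -0.065 | 0.40 |
| 2.5, 0.7 | 0.60, 1.10 | 1.065 | 0.943 | -0.122 | 0.76 |
| 2.5, 0.7 | 0.60, 1.10, with subgroup main effect* | 1.027 | 0.880 | -0.155 | 0.97 |

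*Subgroup HR 2.0 on CV death and 1.5 on HHF.

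Example: ln 0.943 − ln 1.065 = -0.059 − 0.063 = -0.122. In that row the HHF HRs of 0.675 and 0.719 become 0.718 and 0.677, so the order of the subgroups reverses. The both-hazards ratios scatter around 1.00 with SE about 0.16 × √(3600/40000) = 0.05. The shift is a paired difference on the same data and is much less noisy.

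**What drives the shift.** Adding the subgroup main effect, but not the interaction, to the CV-death hazard does not help. The ratios in the fifth, sixth and seventh rows become 0.917, 0.936 and 0.868. The missing interaction is the cause.

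**False rejection.** For a shift of d SE, a nominal 5% two-sided interaction test rejects with probability Φ(−1.96 + d) + Φ(−1.96 − d):
- d = 0.40: 6.9%
- d = 0.76: 11.8%
- d = 0.97: 16.3%

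**Milder heterogeneity.** Two further simulation sets used theta 2 and alpha 0.8. For CV-death HRs 0.85 versus 1.05 they gave shifts of about -0.02 and -0.04. Divided by 0.16, that is 0.12 to 0.25 SE, or 5.2% to 5.7% rejection. For 0.70 versus 1.20 they gave -0.075 (25 trials of 2400 patients, SE of the paired difference 0.009) and -0.10 to -0.12 (20,000 patients).

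**Outside this range.** Theta 4 and alpha 1.2 with CV-death HRs 0.60 versus 1.10 gave -0.20 (1.07 SE). That fit returned theta 3.34, so I take from it only that a stronger link enlarges the shift.

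**The case against.** **The SAP does not say *only*.** The phrase could loosely mean the whole joint model. That is fair, and the point rests on the literal reading. The section's own vocabulary favours that reading, and nothing in it places the terms in the CV-death hazard.

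**Age and eGFR.** A reader might infer that the CV-death hazard loses age or eGFR altogether when these are categorised. That needs a narrow reading of the sentence that adds the category and a broad reading of the sentence that drops the covariate. Read narrowly throughout, the continuous covariate stays in the CV-death hazard. Read broadly throughout, the category replaces it in both. The dropping sentence also appears for the Cox and eGFR-slope subgroup models, which have a single part. What stands is that the text does not say which hazard is meant.

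**Missing main effects.** A reader might also infer harm because NYHA class or recent HHF would have no effect on CV death in the model. A main effect alone moved the treatment interaction by only +0.012. It does distort the subgroup's own prognostic coefficient (about 1.45 fitted for a true 1.6 in one simulation), but that is not a treatment effect. For subgroups already among the covariates, such as sex or diabetes status, the main effect is in both hazards and only the interaction is missing.

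**Direction.** The bias does not always flatter the drug. Its sign depends on alpha, which the SAP estimates and allows to be negative. With alpha positive, one subgroup looks better and the other worse.

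**Relevance.** The analyses are exploratory, and CV death by subgroup is planned separately, so heterogeneity would be visible. Both facts limit the consequence. Neither corrects the HHF estimates.

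**Conclusion.** The point holds for the literal wording and is a cheap improvement. The subgroup HHF HRs from the joint model are biased when two conditions meet: alpha is not zero, and the treatment effect on CV death differs by subgroup. Under the assumptions above, the bias is small for mild heterogeneity and reaches about 1 SE of the interaction when the CV-death HRs are far apart. At that size it can reverse the apparent order of two subgroups. These magnitudes depend on assumed theta, alpha and event rates, and on models simpler than the SAP's. They show the mechanism and its order of size and do not predict this trial's result.

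It would be wrong to conclude that the key secondary result is compromised. The confirmatory recurrent-HHF model has the same covariates in both hazards and no subgroup terms.

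**What to change.** In SAP 7.5.1.1, state that the subgroup term (where it is not already a covariate) and the subgroup-by-treatment term enter both the recurrent-HHF and the CV-death hazards. State also that when age or eGFR is replaced by its categories, the replacement is made in both hazards. Showing the subgroup CV-death HRs beside the HHF HRs would help readers, and those analyses are already planned.

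The cost is two sentences and a few parameters in the CV-death hazard:
- a binary subgroup outside the covariate list, such as NYHA class: 1 main effect + 1 interaction = 2
- race with four categories: 3 + 3 = 6
- region, already a five-level covariate: 4 interactions

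The downside is possible convergence trouble where a subgroup has few CV deaths. SAP 7.4.4 already leaves out of the primary-endpoint model any subgroup with fewer than 14 patients with events. A similar minimum counted on CV deaths could be used here.
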